1. INTRODUCTION

1.1 Prostate Cancer

Prostate cancer is the most commonly diagnosed cancer in American men, and the second leading cause of cancer death. Statisticians at the National Cancer Institute estimate that there will be 233,000 new cases of prostate cancer and 29,480 deaths from prostate cancer in 2014 (seer.cancer.gov/statfacts/html/prost.html). Since the prostate specific antigen (PSA) test became commercially available in 1985, most prostate cancers have been discovered through PSA screening. Widespread PSA screening for prostate cancer has resulted in a migration to a lower stage of prostate cancer. For example, rates of lymph node metastasis at diagnosis have declined from 20% in the 1970s and 1980s to less than 4% today. Imaging to detect the presence and location of metastatic prostate cancer has historically relied on the ^{99m}Tc -MDP bone scan and cross-sectional imaging with a CT scan or MRI. In addition to imaging studies, nomograms based on clinical T stage, PSA level, PSA kinetics, Gleason grade, and volume of cancer in biopsy specimens are used to predict the risk of metastasis (Stephenson AJ, Sacrdino, PT, Eastham, JA et al., 2006). More recently, positron emission tomography (PET) using radiopharmaceuticals such as ^{11}C -choline and ^{11}C -acetate has improved detection of metastatic prostate cancer.

1.2 Prostate Cancer Imaging

1.2.1 Relapsed Prostate Cancer

A rising PSA occurs in approximately 20 to 40% of patients within 10 years of definitive treatment of prostate cancer and is known as a biochemical relapse. A biochemical relapse of prostate cancer usually precedes evidence of relapse using conventional imaging. The definition of biochemical relapse after radical prostatectomy is a PSA of 0.2 ng/mL confirmed at that level or a higher level on a subsequent PSA test 3 months later (Cookson MS, Aus G, Burnett AL, et al, 2007). The definition of biochemical relapse after radiation therapy is a PSA level 2 ng/mL above the nadir level after treatment (Roach M, Hanks GE, Thames H, et al, 2006). PSA kinetics, most commonly the PSA doubling time; the initial stage and grade of prostate cancer; and time from treatment to biochemical relapse can be used to predict localized versus metastatic cancer states. However, early identification on imaging studies of relapsed prostate cancer is essential in treatment planning. Results of studies using ^{11}C -choline PET/CT and ^{11}C -acetate PET/CT have shown high sensitivity and specificity at low PSA levels in men with biochemical relapse after primary treatment for prostate cancer.

Two early studies have shown that ^{11}C -acetate PET is more sensitive than ^{18}F -FDG PET in detection of relapsed prostate cancer (Oyama N, Akino H, Kanamaru H, et al, 2002; Fricke E, Machtens S, Hofmann M, et al, 2003). In a study ^{11}C -choline PET/CT in 41 patients with biochemical relapse after radical prostatectomy sensitivity was 89% with PSA levels < 2.5 ng/mL (Rinnab L, Simon J, Hautmann

Investigatory New Drug
**Clinical Trial Protocol:
Choline C11 Injection**

Revision Date: _01/30/2015

Page 8 of 59

RE, et al, 2009). In a larger study of 190 patients with biochemical relapse after radical prostatectomy, ^{11}C -choline PET/CT detection of prostate cancer was correlated with the PSA level (known as the trigger PSA) and with PSA kinetics. Trigger PSA levels were significantly different between PET-positive and PET-negative patients ($P=0.0001$), and ROC analysis showed an optimal trigger PSA cutoff value of 2.43 ng/mL. Using multivariable analysis, trigger PSA and PSA velocity were independent prediction factors for a positive PET, whereas PSA doubling time was an independent factor for a positive PET scan only in patients with a trigger PSA < 2.0 ng/mL. An important finding of this study was that Gleason grade, pathologic tumor stage and lymph node status, and time from radical prostatectomy to biochemical relapse were not independent prediction factors for a positive PET (Castellucci, P, Fuccio C, Nanni C, et al, 2009).

In a retrospective review reported by the Mayo Clinic, 176 patients with biochemical relapse of prostate cancer after primary treatment underwent ^{11}C -choline PET/CT imaging. Lesions were identified in 32% of the patients by ^{11}C -choline PET/CT which were not detected by conventional imaging. Investigators reported an optimal trigger PSA level 2.0 ng/mL. In this study, a true positive scan was confirmed by pathology of targeted biopsies or of surgical specimens (41.4%), or by conventional imaging. Performance characteristics were sensitivity 93%, specificity 76%, positive predictive value 91% and negative predictive value 81%. This study was limited by the retrospective nature of the data collection and the investigators recognized that prospective studies are needed to compare ^{11}C -choline PET to conventional imaging with bone scan, CT and pelvic MRI (Mitchell, C, Lowe V, Rangel L, et al, 2013).

The choline analog tracer ^{18}F -FCH has been studied in patients with biochemical relapse of prostate cancer with less favorable results than ^{11}C -choline. In a study of 100 patients with biochemical relapse, 89% of patients with trigger PSA < 4 ng/mL were PET negative (Cimitan M, Bortolus R, Morassut S, et al, 2006). In a subsequent study using ^{18}F -FCH in 56 patients with biochemical relapse after radical prostatectomy, sensitivity was 44% when the trigger PSA ranged from 1 to 4 ng/mL (Pelosi E, Arena V, Skanjeti A, et al, 2008).

As ^{11}C -choline has emerged as a favorable diagnostic agent in patients with prostate cancer relapse, studies have been initiated to determine the best imaging modality. ^{11}C -choline PET/CT was compared with ^{11}C -choline PET/MRI in 31 with biochemical relapse. The detection rate for localized relapse was higher and more conclusive for PET/MR which detected 17 regions in 12 patients compared to PET/CT which detected 12 regions in 8 patients. Similar improvements of using MR were also found in detection of lymph node metastases and bone metastases (Eiber M., Souvatzoglou M., Maurer T., et al, 2013).

Investigatory New Drug
**Clinical Trial Protocol:
Choline C11 Injection**

Revision Date: _01/30/2015

Page 9 of 59

1.3 Rationale for Study

Studies of molecular imaging in patients with prostate cancer have shown the following:

1. ^{11}C -choline, ^{18}F -fluorocholine (^{18}F -FCH), and ^{11}C -acetate have shown greater accuracy in prostate cancer staging than conventional imaging or ^{18}F -FDG PET.
2. ^{11}C -choline PET and whole body MRI are complementary, and when combined have the highest sensitivity and specificity in detection of prostate cancer metastasis.
3. ^{11}C -choline has the highest sensitivity at low PSA levels for detection of prostate cancer in men who have a biochemical relapse after primary treatment.
4. ^{11}C -choline PET/CT and PET/MRI are complementary and show the highest sensitivity and specificity in detection of lymph node metastasis when combined.

In patients with biochemical relapse of prostate cancer after primary treatment, early localization of cancer with molecular imaging using ^{11}C -choline PET/CT and PET/MRI can lead to improved treatment planning with observation, local-regional therapy, or with systemic therapy. Molecular imaging using PET drug products and PET imaging techniques have the potential to change the paradigm for treating men with biochemical relapse after radical prostatectomy. In a study of 72 men with biochemical relapse and ^{11}C -choline PET/CT positive lymph node metastasis, salvage lymphadenectomy resulted in a 5-year relapse-free survival of 35% and cancer-specific survival of 75% (Rigatti P, Suardi N, Briganti, A, et al, 2011). Response to treatment can be monitored with PET molecular imaging as well as with PSA, which may lead to earlier additional therapy.

In March 2013, the FDA approved the New Drug Application (NDA) of the Mayo Clinic in Rochester, MN, for the use of ^{11}C -choline as a radiopharmaceutical agent for PET imaging of patients with suspected prostate cancer relapse. ^{11}C -choline has a half-life of 20 minutes, which limits the distribution of the product to Rochester, MN, and the surrounding area. As a result, this diagnostic agent and its associated benefits have limited availability to patients.

The key objective of this study is to provide expanded access to this drug product as currently defined under the reference listed drug label as an investigational drug in geographical service areas where ^{11}C -choline is not available. Under the current label, ^{11}C -choline is approved for use in conjunction with both CT and MR imaging modalities. However, sufficient data does not exist to determine which modality is most efficacious and under what conditions. It is the intention of the study sponsor to image each patient using GE's Trimodality Imaging System that combines PET, CT, and MR techniques to provide PET/CT and PET/MR fused images. As a result, the patient will benefit from the most useful and deterministic imaging information.

Investigatory New Drug
**Clinical Trial Protocol:
Choline C11 Injection**

Revision Date: _01/30/2015

Page 10 of 59

2. STUDY OBJECTIVES

Based on these rationales, this clinical trial will address the following objectives:

- A. Provide expanded access the drug ^{11}C -choline.
- B. Determine the performance characteristics (sensitivity, specificity, positive predictive value, negative predictive value) of ^{11}C -choline PET/CT and PET/MRI in the detection of metastatic prostate cancer in patients with biochemical relapse of prostate cancer after primary treatment in a prospective manner.
- C. Determine the optimal PSA trigger value in ^{11}C -choline PET/CT and PET/MRI positive patients through a prospective study.
- D. Determine factors that predict a confirmed positive ^{11}C -choline PET/CT and PET/MRI using a multivariable analysis of clinical and pathologic data collected prospectively.
- E. Compare the individual performance characteristics of ^{11}C -choline PET/CT and ^{11}C -choline PET/MRI and the combination of ^{11}C -choline PET/CT and PET/MRI

3. ETHICS

3.1 Institutional Review Board

An Investigational Review Board (IRB) will assess and approve the Investigatory New Drug (IND) application. This will include approval of the IND Protocol, Investigator's Brochure, and the Informed Consent. The Principal Investigator and Sponsor will provide the IRB with appropriate reports on the progress of the study, including safety updates, in accordance with applicable FDA regulations and in agreement with policy defined by sponsor and as outlined in this protocol. All amendments to the study will be sent to the IRB for information (minor amendment) or for approval (major amendment) before implementation of the study amendments.

Decatur Memorial Hospital (DMH) and the Cancer Care Institute (CCI, an affiliate of DMH) are both located in Decatur, Illinois. The Decatur Memorial Hospital Institutional Review Board (DMH IRB) will be involved in all aspects of study planning and considerations as per 21 CFR part 56. The DMH IRB is covered under Decatur Memorial Hospital's Federal Wide Assurance (FWA) # of 00006097. The DMH IRB reviews research projects which involve human participants to ensure that two broad standards are upheld: first, that participants are not placed at undue risk; second, that they give un-coerced, informed consent to their participation.

Investigatory New Drug
**Clinical Trial Protocol:
Choline C11 Injection**

Revision Date: _01/30/2015

Page 11 of 59

3.2 Ethical Conduct of Study

The study shall be performed in accordance with Health Insurance Portability and Accountability Act (HIPAA) regulations, Food and Drug Administration (FDA) Good Clinical Practice (GCP) regulations as defined within the Code of Federal Regulations, 21 CFR parts 50, 56, and 312 and clinical safety data management (E2A) regulations. The Principal Investigator / Sponsor shall provide the IRB with all relevant material, including copies of the IND protocol, Informed Consent, Investigator's Brochure and any subject information or advertising materials. The study shall not be initiated until the IRB provides written approval of the protocol and the informed consent.

Each study subject shall be required to provide written authorization that their patient information can be disclosed and used by the Principal Investigator and other researchers as well as the Sponsor for the purposes of assessing the efficacy of the study drug and imaging protocol.

3.3 Patient Information and Informed Consent

In compliance with the requirements set forth by the FDA in 21 CFR Part 50, a properly written and executed Informed Consent shall be obtained from each study subject prior to enrollment and initial screening evaluations required by this protocol. The IC has been reviewed by the Sponsor for acceptability and shall be presented by the Principal Investigator, together with the IND protocol and Investigator's Brochure, to the IRB for review and approval prior to the start of the study. The IC shall be written in such a way as to be fully comprehensible by the prospective study participant.

The Informed Consent shall be revised in the event new information becomes available during the study that may be relevant to the subject. Any revision shall be submitted to the IRB for review and approval before use.

It is the Principal Investigator's responsibility to obtain a properly written and executed Informed Consent from the study subject only after there has been an adequate explanation of the goals, methods, anticipated benefits and potential hazards of the study. The subject shall be given ample time to inquire about details of the study and decide whether to participate in the study. The IRB-approved IC shall be signed and dated by the subject and by the person conducting the informed consent discussion. A copy of the properly executed IC shall be provided to the study subject. The original signed informed consent shall be kept in a confidential location on site.

Investigatory New Drug
**Clinical Trial Protocol:
Choline C11 Injection**

Revision Date: _01/30/2015

Page 12 of 59

4. STUDY PATIENTS

4.1 Patient Study Population

Decatur Memorial Hospital (DMH), a not-for-profit division of Illinois Health & Science, will be the site designated for imaging the study subjects and evaluating the ^{11}C -choline PET/CT and PET/MR imaging data. Patients will be referred from within the institution as well as from outside treatment organizations. Urology, radiation oncology and medical oncology practices within an approximately 300 mile radius of the DMH imaging center will be contacted for enrollment of patients into this study. As such, this study will encompass patients being served in major cities, such as Chicago, St. Louis, Cincinnati, Louisville and Indianapolis who would otherwise have to seek ^{11}C -choline PET imaging at the Mayo Clinic in Rochester, MN. In the event that patients outside of the recruitment area wish to enroll in the clinical trial, they will also be considered. A primary source for patients will also be from The Cancer Care Institute, also a not-for-profit division of Illinois Health & Science. This phase III study is planned to provide expanded access to as many patients who elect to participate in the study that are over the age 18 and have experienced a biochemical relapse of prostate cancer after primary treatment.

4.1.1 Inclusion Criteria

Patients must meet all of the following criteria:

1. For biochemical relapse after primary treatment
 - a. PSA ≥ 0.2 ng/ml after radical prostatectomy confirmed at that level or higher on a subsequent test 3 months later
 - b. PSA increase ≥ 2 ng/ml from nadir following radiation therapy
 - c. PSA increase ≥ 2 ng/ml from nadir following radiation therapy plus androgen deprivation therapy with nadir defined with normalized testosterone level
 - d. Two consecutive PSA increases from nadir level after androgen blockade or androgen suppression therapy
2. Kidney function with GFR ≥ 60 mL/sec/1.73m² and Creatinine < 1.7 mg, collected within 90 days of planned scan
 - a. if GFR is $>$ or equal to 60 mL/sec/1.73m², PET/CT will be completed with contrast
 - b. if GFR is < 60 mL/sec/1.73m², PET/CT will be completed without contrast
 - c. if Creatinine is $>$ than 1.7 mg, Radiology will follow ACR recommendations as outlined in department policy
3. No known allergy to iodinated radiologic contrast media
4. Able to have MRI based on screening evaluation

Investigatory New Drug
**Clinical Trial Protocol:
Choline C11 Injection**

Revision Date: _01/30/2015

Page 13 of 59

if patient is found to be MRI incompatible, the ¹¹C-choline PET/MRI portion of the study will not be completed. These patients will not be included in the comparison data, but will have access to ¹¹C-choline PET/CT scan.

5. ECOG Performance Status of 0, 1, or 2

4.1.2 Exclusion Criteria

Patients will be excluded if any of the following criteria are met:

1. ECOG Performance Status > 2.
2. Concurrent malignancy, i.e. colon cancer.
3. Treatment for another malignancy except superficial skin cancer within 5 years

4.2 Subject Withdrawal And Replacement

4.2.1 Criteria For Subject Withdrawal

Subject participation may be withdrawn / discontinued for the following reasons (but not limited to):

1. Patient request for any reason to discontinue participation within the clinical trial.
2. Patient non-compliance with the accepted protocol.
3. Suspension or discontinuation of the clinical trial by the Sponsor, Zevacor Molecular.

4.2.2 Procedures for Subject Withdrawal

Study patients who decide to discontinue the protocol and withdraw from the clinical trial will be seen and assessed by an Investigator. The reason(s) for the withdrawal and the date of the withdrawal will be documented in the study records for the patient.

If death is the reason for the withdrawal from the clinical trial, there are two options for categorizing as such: 1) progressive disease, or 2) a Serious Adverse Event (SAE). Although more than one SAE may be documented as reason for withdrawal, only one SAE will be documented as the cause of death.

At withdrawal, all on-going study-related AEs and SAEs must be followed until resolution, unless in the Investigator's opinion the condition is unlikely to be resolved due to the patient's underlying disease.

5. INVESTIGATIONAL PLAN

5.1 Study Protocol

1. The study will consist of patients who have a biochemical relapse or other evidence of relapse after primary treatment. This study group will consist of patients who have been treated with radiation therapy, or androgen suppression and radiation therapy who have a PSA \geq 2 ng/mL higher than the nadir level. The nadir level in patients who have been treated with androgen suppression and radiation therapy is determined after the serum testosterone level has normalized. This study group will also consist of patients who have been treated with radical prostatectomy and who have a biochemical relapse defined as a PSA of 0.2 ng/mL confirmed at that level or higher on a subsequent PSA test 3 months later. This group may consist of men who have other clinical evidence of relapse such as a suspicious bone scan or CT scan regardless of PSA kinetics. Patients identified as potential subjects will be screened against the eligibility criteria as defined above in Section 4.1.
2. Informed consent will be obtained from all participants before any study related procedures are conducted. Each participant will be informed about the nature of the study, its purpose, and possible risks. Informed consent will be documented by using the written informed consent document approved by the local IRB at the Decatur Memorial Hospital.
3. At the time of referral, patients will be asked to bring their prior records as it pertains to their prostate cancer history. Data collected from outside records, such as radiographic studies, previous imaging studies and biopsies will be incorporated into the study record.
4. Abstracted data for the study record will include:
 - a. Patient demographics such as age, race, and family history of prostate cancer
 - b. Risk factors such as finasteride or dutasteride use, and environmental exposure
(eg. Agent orange)
 - b. Prostate exam results, most recent within last 90 days
 - c. PSA test results, most current and past
 - d. Past medical and surgical history
 - e. Current medications
 - f. Allergies
 - g. Pathology reports
 - h. Imaging reports
 - i. Date of diagnosis
 - j. Date(s) of biochemical relapse and coordinating PSA results

Once all records have been assessed for eligibility, an order for the ^{11}C -choline PET CT scan and MRI scan will be requested from the referring physician and patient will be scheduled and given the appropriate prep instructions.

5. Patients entered into the study will undergo a ^{11}C -choline PET CT scan and MRI scan. The CT scan will be performed with intravenous contrast unless deemed unsafe by lab values. The CT and MRI images will be evaluated for evidence of metastatic prostate cancer. The ^{11}C -choline PET CT and MRI images will be evaluated for evidence of metastatic prostate cancer. Unequivocal evidence of metastasis on both conventional imaging and ^{11}C -choline PET will be considered a true positive. Evidence of metastasis on conventional imaging or ^{11}C -choline PET will be confirmed with biopsy or surgical pathology when possible, or by response to treatment on subsequent imaging. If confirmation of metastasis is not achievable by biopsy or surgical pathology, then confirmation will be achieved with ^{11}C -choline PET CT and MRI images obtained 3 months after treatment conclusion. Rates of confirmed metastasis between conventional CT and MRI images will be compared with the ^{11}C -choline PET CT and MRI images.
6. Upon conclusion of each imaging protocol, the referring physician will receive written documentation of the results. At this time, the patient will be considered off study and no further follow up is required.

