5.4.2 Image Assessment Criteria

The following image criteria will be documented with each patient study utilizing the worksheets included as attachments in appendix A3.0.

- Lesion considered positive if there is focal uptake greater than background.
- Faint uptake within inguinal nodes considered normal.
- Retroperitoneal lymph nodes >1 cm in short axis diameter considered positive.
- Record CT abdomen and pelvis as follows:
 1. Report mass within prostate or prostate bed
 2. Report retroperitoneal lymph nodes with >1 cm short-axis measurement
 3. Report bone metastases
 4. Report any other metastatic disease (liver, lung, etc)
- Record PET/CT as follows:
 1. Study quality (adequate, non-diagnostic)
 2. Positive lymph nodes.
 - Pelvic or retroperitoneal lymph nodes >1 cm.
 - Radiotracer uptake in lymph node any size
 3. Bone metastases
 - Radiotracer uptake
 - CT abnormality
 4. Other metastatic disease (liver, lung, etc.)
 - Radiotracer uptake
 - CT abnormality
 5. Confidence of diagnosis: 3 – 1
(Rating: 3 – Definitely Present, 2 – Probably Present, 1 – Equivocal)
- Record PET/MRI:
 1. Study quality (adequate, non-diagnostic)
 2. Positive lymph nodes.

- Retroperitoneal lymph nodes >1 cm.
- Radiotracer uptake any size lymph node
- DWI positive
- 3. Bone metastases
 - Radiotracer uptake
 - T2 or DWI positive
- 4. Other metastatic disease (liver, lung, etc.)
 - Radiotracer uptake
 - T2 or DWI positive
- 5. Confidence of diagnosis: 3 – 1
(Rating: 3 – Definitely Present, 2 – Probably Present, 1 – Equivocal)

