5.5 Study Data – Statistical Analysis

- Sample Size:

This study is designed to compare fused ¹¹C-choline PET/CT and MRI scans against a standard CT scan and MRI scan. Based on the literature, the group detection rates are approximately 50%. In this study a 20 percentage point increase (eg: from 15 – 35 percent) in detection rate is the desired goal. The study is a paired design, in that each procedure will be performed on each individual. The important performance characteristics of these tests, including sensitivity, specificity, positive predictive value, and negative predictive value will be examined within this study. A sample size estimate was derived using a p-value of 0.05, a power of 80 %, and a paired chi square test for proportions. It was further assumed that the false positive rate is about 4 % and the false negative rate is about 20 %, which are similar to the literature. This would indicate approximately 66 pairs of data. To compare, an independent chi square test would indicate about 71 subjects per group for a comparable 20 point change. Increasing the sample size by 10 percent, for attrition, would increase the number of paired samples to about 73. Increasing the number of pairs to 100 will provide some flexibility on the false positive and false negative rates.

While more than 100 patients may be admitted into the study under expanded access, for the purposes of the comparison study and resulting data analysis, only the first 100 qualified patients will be admitted into the study and included in the study data.

- Data Analysis:

1. True positives will consist of evidence of metastatic prostate cancer on conventional CT or MRI images or on ¹¹C-choline PET/CT or MRI images confirmed with biopsy, surgical

pathology, or by response to treatment with androgen suppression or other medical or radiation therapy.

2. True negatives will consist of negative images.
3. False positive will consist of evidence of metastatic prostate cancer on conventional CT or MRI images or on ^{11}C -choline PET/CT or MRI images, but without corresponding confirmation from biopsy, surgical pathology or response to treatment.
4. False negative will consist of negative images, but with positive biopsy, surgical pathology or a response to treatment.
5. Sensitivity, specificity, PPV, and NPV of CT and MRI and of ^{11}C -choline PET/CT and MRI will be calculated
6. Performance characteristics between ^{11}C -choline PET/CT and PET/MRI will be compared.

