6.2 Warnings and Precautions

- Imaging errors have been reported during previous clinical studies with ^{11}C -choline PET and PET/CT imaging. A negative image does not rule out the presence of recurrent prostate cancer and a positive image does not confirm the presence of recurrent cancer. ^{11}C -choline uptake is not specific

Investigatory New Drug
**Clinical Trial Protocol:
Choline C11 Injection**

Revision Date: _01/30/2015

Page 20 of 59

for prostate cancer and may occur with other types of cancer, such as lung carcinoma and brain tumors.

- Blood PSA levels < 2 ng/mL have been associated with poor performance ^{11}C -choline PET imaging, with indications of higher numbers of false positive and false negative results.
- Tissue inflammation as well as prostatic hyperplasia have been associated with false positive ^{11}C -choline PET images.
- Concomitant colchicine or androgen-deprivation therapeutic drugs, such as luteinizing hormone-releasing analogs and anti-androgen drugs, may interfere with ^{11}C -choline PET imaging. One published report of ^{18}F methylcholine PET imaging indicated that discontinuation of colchicine for two weeks resolved the colchicine effect. The impact of discontinuation of androgen-deprivations therapy upon ^{11}C -choline PET imaging has not been established.

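### An unconfirmed man positive on both conventional imaging and choline PET is a true positive in section 5.1 and a false positive in section 5.5, so specificity and PPV are not uniquely defined

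*Combined protocol and SAP*

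**What the plan says.** All references are to the main (comparison) protocol in the combined protocol and SAP. The expanded access protocol bound with it plans no analysis and is not affected.

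- Section 5.1 item 5: "Unequivocal evidence of metastasis on both conventional imaging and ^{11}C -choline PET will be considered a true positive". The next sentence says that evidence on conventional imaging or PET "will be confirmed with biopsy or surgical pathology when possible, or by response to treatment on subsequent imaging". Where pathology cannot be obtained, confirmation comes from "PET CT and MRI images obtained 3 months after treatment conclusion".
- Section 5.5, Data Analysis item 1: a true positive is evidence on either kind of imaging that is confirmed by biopsy, surgical "pathology, or by response to treatment with androgen suppression or other medical or radiation therapy".
- Section 5.5, Data Analysis item 3: a false positive is evidence on either kind of imaging "but without corresponding confirmation from biopsy, surgical pathology or response to treatment". Neither item makes an exception for agreement between tests.
- Section 5.4.1 item 10: the blinded reads are compared with histology or post-treatment imaging. Agreement between tests is not listed.
- Section 5.4.2, PET/CT record: "Pelvic or retroperitoneal lymph nodes >1 cm" is an entry of its own, apart from tracer uptake. Section 5.2 describes one CT, fused with the PET.
- Section 6.2: "a positive image does not confirm the presence of recurrent cancer".

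No section says which rule governs.

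**The concern.** Take a man with clear findings on both CT/MRI and choline PET who has no biopsy, no surgery and no documented treatment response. Section 5.1 makes him a true positive; section 5.5 makes him a false positive. Objective B asks for sensitivity, specificity, PPV and NPV, and this man changes several of them.

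The 5.1 rule also has a bias of its own. For double-positive men the index test and its comparator together act as the reference standard, so an unequivocal false positive shared by both tests can never be recorded as one. The two reads are not separate evidence either. They share a CT, and an enlarged node can be entered on the PET/CT record without uptake. A large benign node could be positive on both reads and so confirm itself.

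Because the plan does not choose between the rules, the choice could be made after the results are known.

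**Working it through.** **1. The plan's own sample size.** Inputs from section 5.5: alpha 0.05 (two-sided assumed), power 80%, paired chi-square, error rates 4% and 20% used as the two discordant cells. The unpooled formula gives n = (1.960 + 0.842)² × (0.24 − 0.16²) / 0.16² = 65.7. Enumerating the power of the uncorrected McNemar test first reaches 0.80 at 66 pairs. The independent-groups figure reproduces as 70.9 (arcsine, 15% against 35%), and 66 × 1.10 = 72.6, or about 73. The stated 66, 71 and 73 are reproduced. (Cells of 4% and 20% imply a net 16 points, not 20; that is a separate matter.)

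**2. Scoring the same 100 men under each rule.** From section 5.5: 100 men analysed; detection 15% conventional and 35% PET; double-negative men are true negatives (item 2). Assumptions not in the documents:
- conventional-only positives 0% or 4%;
- a second setting of 30% and 50%, placing PET at the plan's approximate 50% with the same 20-point gap;
- 90% of single-positive men confirmed;
- 10%, 25% or 50% of double-positive men unconfirmed, all with unequivocal findings.

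Worked case: 15%/35%, 4% conventional-only, 25% unconfirmed.
- Double positive 15 − 4 = 11; PET-only 35 − 11 = 24; conventional-only 4; double negative 61.
- Unconfirmed double positive U = 0.25 × 11 = 2.75, leaving 8.25 confirmed.
- PET-only: 21.6 confirmed, 2.4 not. Conventional-only: 3.6 confirmed, 0.4 not.

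PET under 5.1: TP = 11 + 21.6 = 32.6, FP = 2.4, FN = 3.6, TN = 61.4. PPV = 32.6/35 = 93.1%; specificity = 61.4/63.8 = 96.2%.

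PET under 5.5: TP = 8.25 + 21.6 = 29.85, FP = 5.15. PPV = 29.85/35 = 85.3%; specificity = 61.4/66.55 = 92.3%.

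Conventional: PPV 14.6/15 = 97.3% against 11.85/15 = 79.0%; sensitivity 14.6/36.2 = 40.3% against 11.85/33.45 = 35.4%.

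Difference in confirmed detections: 32.6 − 14.6 = 18.0 under 5.1 and 29.85 − 11.85 = 18.0 under 5.5.

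**3. Range (5.1 rule → 5.5 rule, %).**

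| Detection (conv-only) | Unconfirmed | PET PPV | PET spec. | Conv. PPV | Conv. sens. | PET sens. |
|---|---|---|---|---|---|---|
| 15/35 (4) | 10% | 93.1→90.0 | 96.2→94.6 | 97.3→90.0 | 40.3→38.5 | 90.1→89.7 |
| 15/35 (4) | 25% | 93.1→85.3 | 96.2→92.3 | 97.3→79.0 | 40.3→35.4 | 90.1→89.2 |
| 15/35 (4) | 50% | 93.1→77.4 | 96.2→88.6 | 97.3→60.7 | 40.3→29.6 | 90.1→88.3 |
| 30/50 (4) | 50% | 95.2→69.2 | 95.1→75.1 | 98.7→55.3 | 57.8→43.5 | 93.0→90.6 |
| 30/50 (0) | 50% | 96.0→66.0 | 96.2→74.6 | 100→50.0 | 62.5→45.5 | 100→100 |

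The PPV shift is simply U divided by the number of test positives (2.75/35 = 7.9 points for PET, 2.75/15 = 18.3 for conventional), so it does not depend on the 90% assumption. The specificity shifts do. The detection difference is 18.0 points under both rules throughout, because a double-positive man adds equally to both tests.

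**The case against.** The strongest reply is that 5.1 contains one stray sentence. The sentence after it asks for confirmation of evidence on conventional imaging or PET, which can be read to include men positive on both; the same paragraph ends by comparing confirmed rates; and sections 5.4.1 and 5.5 have no agreement rule. That reading is possible, but it leaves the quoted sentence with no function, and if the reading is wrong the conflict with 5.5 stands. The text needs an edit either way.

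The word unequivocal also limits the rule, and this stands: equivocal agreement is not covered, and the rule is not written per lesion. But the term is not operational for both tests. Section 5.4.2 gives a 3–1 confidence rating for PET/CT and PET/MRI and none for the conventional CT record. Counting every double positive as unequivocal makes the sizes above upper values for a given unconfirmed share.

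The shared-CT argument is clearest for nodes over 1 cm. For bone and other disease, uptake and CT abnormality are listed with no and/or rule, so self-confirmation there is possible but not shown. The section 6.2 warning is general and does not address agreement between modalities.

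A reader might try to size the bias from the retrospective series in section 1.2.1 (sensitivity 93%, specificity 76%, PPV 91%). Those figures imply a prevalence of 0.2184/(0.2184 + 0.0837) = 72.3% and about 0.723 × 0.93 + 0.277 × 0.24 = 74% PET-positive, well above the planning rates of 35% or about 50%. That series also accepted conventional imaging as confirmation, so it cannot serve as an unbiased baseline.

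**Conclusion.** The contradiction is real and unresolved. It affects only unconfirmed men with unequivocal findings on both tests: about 1–8 per 100 at 15%/35% and about 3–15 per 100 at 30%/50%, if 10–50% of double positives are unconfirmed. Across the scenarios run, the choice of rule moves PET PPV by about 3–30 points, PET specificity by about 2–22, conventional PPV by about 7–50 and conventional sensitivity by about 2–17. The unconfirmed share is an assumption; the documents give none.

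A reader might infer that Objective B goes unanswered, or that the two tests validate each other throughout. The documents do not support either. PET-only and conventional-only positives need confirmation under both sections, PET sensitivity moves by at most about 2.4 points, and the paired detection difference and the 66-pair calculation are untouched. What fails is that specificity, PPV and conventional sensitivity have two values under the plan as written.

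One limit remains after the sections are reconciled: the fallback confirmation in 5.1 reuses choline PET, so the reference standard is still not fully independent for men confirmed that way.

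**What to change.** Delete the both-positive sentence from section 5.1 item 5. Add one line to section 5.5: men positive on both conventional imaging and choline PET are classified by items 1 and 3, like every other positive. Keep unconfirmed double-positive men in the main 2x2 tables under that rule and report how many there are. Present the both-positive-equals-true-positive scoring only as a sensitivity bound. With everything else fixed, the two scorings bracket any split of these men between true and false.

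Setting these men aside from the main tables is not a good alternative. It conflicts with item 3, and in the worked case it returns PET specificity to 61.4/63.8 = 96.2% and conventional specificity to 63.4/63.8 = 99.4%, exactly the 5.1 values.

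The cost is two small text edits and one extra table, with no new procedures. Reported specificity and PPV may be somewhat lower, and item 3 is conservative for men who have disease but were never confirmed, which is why the count and the bound should be shown.
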